3.4 Baseline Inclusion Criteria

- Medicated diurnal IOP \geq 20 mmHg and \leq 35 mmHg

3.5 Consent

Participation in the study is voluntary. When it has been established that the patient is eligible for possible enrollment into the study, written informed consent (ICF) will be obtained.

3.6 Enrollment

Patients who sign the informed consent form (ICF) are considered enrolled. Study specific exams should be initiated only after ICF is obtained.

4.0 CLINICAL FOLLOW-UP SCHEDULE

All subjects will be scheduled to return for follow-up examinations at defined intervals through 12 months. **Table 5** shows the schedule of events and procedures at each protocol-required visit.

SCHEDULE OF VISITS

| Procedure | Screening ¹ | Baseline (30 days from Scr) | Surgery (30 days from BL) | 1D Postop (+/- 2D) | 7D Postop (+/- 2D) | 1M Postop (30+/- 7D) | 2M Postop (60+/- 10D) | 3M Postop (90+/- 14D) | 6M Postop (183+/- 14D) | 9M Postop (274+/- 30D) | 12M Postop (365+/- 45D) |
|---|------------------------|--------------------------------|------------------------------|-----------------------|-----------------------|-------------------------|--------------------------|--------------------------|---------------------------|---------------------------|----------------------------|
| Informed Consent | X | | | | | | | | | | |
| Medical History Ophthalmic and Non-Ophthalmic | X | | | | | | | | | | |
| Medication Assessment | X | X | X | X | X | X | X | X | X | X | X |
| Manifest Refraction | X | X | | X | X | X | X | X | X | X | X |
| BCVA - Snellen | X | | | | | | | | | | |
| Visual Acuity-Pinhole | | | X | | | | | | | | |
| BCVA - ETDRS | | X | | | X | X | X | X | X | X | X |
| Intraocular Pressure Goldmann Applanation Tonometry | | X | | X | X | X | X | X | X | X | X |
| Diurnal Intraocular Pressure Goldmann Applanation Tonometry | | | X ³ | | | | | | | | X ³ |
| Intraocular Pressure 2 to 6 hours after surgery | | | | X ⁴ | | | | | | | |
| Pachymetry CCT | X | | | | | X | X | X | X | X | X |
| Gonioscopy | X | | | | | X | X | X | X | X | X |
| Slit Lamp Exam | X | X | | X | X | X | X | X | X | X | X |
| Lenticular Opacity Grading | X ⁵ | | | | | X ⁵ | | | X ⁵ | | X ⁵ |
| Visual Field Humphrey 24-2 SITA Standard | X | | | | | | X | X | X | X | X |
| Fundus Exam/Disc Evaluation | X | | | | | | X | X | X | X | X |
| Optic Disc Photography | X | | | | | | | | | | X |
| Subject Questionnaire | X | | | | | | | X | | | X |
| Hydrus Implantation | | | | X ⁶ | | | | | | | |
| Adverse Event Assessment | | | | X | X | X | X | X | X | X | X |

¹ At the Screening Visit, all assessments will be performed for both eyes.

² At the Baseline Visit, both eyes may be evaluated if eligibility confirmed after all Screening procedures completed.

³ Daytime-Diurnal IOP measurements will be performed 3 times at 8:00 AM (± 1 hour), 12:00 PM (± 1 hour), and 4:00 PM (± 1 hour).

⁴ Single reader method (no masking required) and only one measurement. Goldmann or portable tonometer may be used.

⁵ Phakic subjects only.

⁶ Subjects who do not receive the microstent during surgery will be followed for safety for 1 month postoperatively or until the device-related adverse event, if applicable, has resolved or is stable.

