5.0 STATISTICAL METHODS

5.1 General Data Handling

Descriptive statistics on continuous variables will include mean, standard deviation, median, and range. Confidence intervals will be included for selected endpoints. Categorical variables will be summarized using frequency counts and percentages. A confidence level of 95% will be used for the confidence intervals. Statistical testing will be two-sided with a significance level of 0.05 or one-sided with a significance level of 0.025 unless specified otherwise. Data listings of individual subject data may be provided.

The baseline values are those that are obtained at the closest visit prior to the surgery. The arithmetic difference between the baseline and the postoperative visit are defined as follows:

Change from baseline = postoperative value – baseline value

Percent change from baseline = change from baseline ÷ baseline X 100.

The Safety Population includes all subjects for whom a Hydrus microstent was implanted or implantation was attempted.

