5.2 Study Populations

The **Effectiveness Population** will consist of all the subjects who undergo the Hydrus implantation surgery and are not discontinued early from the study due to unrelated reasons such as death or relocation. The primary analyses on the primary and secondary effectiveness endpoints will be based on the **Effectiveness Population**. The reasons for discontinuation will be reported.

Intent to Treat. The ITT population will include all subjects undergoing Hydrus Microstent implantation surgery. For this study the ITT population is the safety population.

Per Protocol. The Per Protocol (PP) population will include all implanted subjects who meet the following criteria:

- Subject meets all protocol eligibility criteria.
- Subject completes the 12-month visit.
- Subject received secondary surgical intervention (SSI) for controlling IOP will be included and treated as non-responder
- Subjects without adverse events that lower IOP such as cyclodialysis cleft.
- Additional criteria, if any, will be established before the data review and database closure.

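### Does safety-only follow-up of failed implantations leave the primary response rate undefined?

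*Combined protocol and SAP*

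**What the plan says.** Section 4.0 sets a year of visits for everyone: "All subjects will be scheduled to return for follow-up examinations at defined intervals through 12 months". Footnote 6 to its table makes the exception: "Subjects who do not receive the microstent during surgery will be followed for safety for 1 month postoperatively or until the device-related adverse event", where there is one, has cleared or stopped changing. The only postoperative diurnal IOP in the table is at month 12.

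The analysis sets are defined as follows.

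- Safety (section 5.1): "The Safety Population includes all subjects for whom a Hydrus microstent was implanted or implantation was attempted".
- Effectiveness (section 5.2), the set for the primary analyses of the primary and secondary endpoints: "all the subjects who undergo the Hydrus implantation surgery and are not discontinued early from the study due to unrelated reasons", with death and relocation as the examples.
- Intent to treat (section 5.2): "The ITT population will include all subjects undergoing Hydrus Microstent implantation surgery", followed by "For this study the ITT population is the safety population".
- Per protocol (section 5.2): "The Per Protocol (PP) population will include all implanted subjects who meet the following criteria". Only in this list is a subject with secondary surgery for IOP control declared a non-responder.

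Under section 5.3.1 a responder has a fall of at least 20% in mean diurnal IOP at month 12 on no more medications than at baseline. The response rate is taken in the Effectiveness Population with an exact binomial 95% confidence interval. Section 5.3.3 restricts the other effectiveness summaries to available data. Section 5.3.1 contains neither that restriction nor a rule for a missing 12-month value.

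**The concern.** Both parts of the primary endpoint are measured at month 12. A subject who leaves the operating room without the device is released from that visit by design, for a reason tied to failure of the procedure. If that subject is nevertheless in the primary analysis set, the outcome is missing by plan, and the missingness is informative.

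Two analysts could then report different headline figures from the same data. One divides the responders by everyone taken to surgery; the other divides by those who received the device. The second figure can never be the lower one, and it describes a different population: successful implantations rather than patients in whom implantation was tried. Leaving that choice until the data are known would be poor practice in a single-group study whose main result is a rate.

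**Working it through.** **Step 1: who is in the primary set.** The Effectiveness and intent-to-treat definitions use nearly the same phrase about undergoing the surgery. The intent-to-treat set is equated with the Safety Population, which includes attempts. Where the plan means implanted subjects only, as in the per-protocol set, it says so. The Effectiveness Population loses only those who stop for unrelated reasons, and a failed implantation is not of that kind. The better reading is that failed implantations are in.

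**Step 2: how they count once in.** The endpoint is a proportion of subjects showing the required fall, taken in that population. A subject with no documented fall does not meet the definition but still belongs to the denominator. Two features support this. Keeping related discontinuations in the set makes most sense if they count against the device. The limit to available data is written for section 5.3.3 and not for section 5.3.1. The text therefore leans to responders divided by all operated subjects.

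**Step 3: the gap between the two counts.** The plan gives no figure to reproduce: no sample size, failure rate or expected response rate. All inputs below are assumptions. Let N be the number operated on, k the failed implantations and x the responders, with f = k/N and p = x/(N − k).

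- Failures left out: x/(N − k) = p.
- Failures as non-responders: x/N = p(1 − f).
- Difference: p − p(1 − f) = p × f.

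| f | p = 40% | p = 50% | p = 60% |
|---|---|---|---|
| 2% | 0.8 points | 1.0 | 1.2 |
| 5% | 2.0 | 2.5 | 3.0 |
| 10% | 4.0 | 5.0 | 6.0 |

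At p = 70% and f = 10% the gap is 0.70 × 0.10 = 7.0 points. At f = 0 it is zero.

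**Step 4: against the precision of the estimate** (exact 95% intervals, assumed N = 50).

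| Case | Left out | Non-responders | Gap |
|---|---|---|---|
| 2 failures, 24 responders | 24/48 = 50.0% (35.2 to 64.8) | 24/50 = 48.0% (33.7 to 62.6) | 2.0 points |
| 5 failures, 27 responders | 27/45 = 60.0% (44.3 to 74.3) | 27/50 = 54.0% (39.3 to 68.2) | 6.0 points |

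In the first case the shift of 2.0 points sits inside intervals 29 to 30 points wide.

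**Step 5: against the true rate.** If failed implantations would have responded at rate q, leaving them out overstates the all-operated rate by p − [p(1 − f) + q × f] = f × (p − q). With q = 20% and the same ranges this is 0.4 to 4.0 points. With q = p it is zero, and with q above p it changes sign (q = 60%, p = 40%, f = 10%: −2.0 points). Since q cannot be below zero, p × f is the largest overstatement.

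**The case for a change.** The strongest case for acting is that the counting rule is inferred, not written. The plan does state a non-responder rule for secondary surgery, but in the per-protocol list, which failed implantations cannot enter, so it shows that such rules can be spelled out and that this one was not. The per-protocol set is no substitute for an implanted-only analysis either, since it also requires full eligibility, a completed 12-month visit and no IOP-lowering adverse event. The promise that "The reasons for discontinuation will be reported" may make these exits visible but does not fix the denominator. The change in the secondary endpoint, meant to be calculated subject by subject, cannot be calculated for them at all.

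All of this stands as a description of missing detail. It does not show that following the plan gives a wrong answer. The implanted-only rate is itself a legitimate quantity, and the concern would accept either choice if it were stated. The silence also extends to any Effectiveness Population subject without a 12-month value, such as an implanted subject who withdraws for a related reason. Failed implantation is one instance of an ordinary gap in analysis detail. For the mean change, using subjects with 12-month data and giving their number is the obvious course.

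**Conclusion.** The observation is accurate, but no change to the plan follows: it is a gap that analysts would fill sensibly. Read as written, sections 5.1, 5.2 and 5.3.1 lead to failed implantations being kept in the denominator and not counted as responders. An analyst who instead reads the Effectiveness Population as completed implantations only would be reporting a legitimate rate for a different population. Converting one figure to the other needs only the number of failed implantations.

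Section 5.3.1 estimates a rate with a confidence interval against no stated performance goal, so no decision turns on the choice. The gap is zero if no implantation fails, and 0.8 to 6.0 points for assumed failure rates of 2 to 10% and response rates of 40 to 60%. The upper end needs a 10% failure rate, for which the documents offer no support. The safety-only follow-up in footnote 6 is not itself at fault. This conclusion rests on the public text, in which membership of failed implantations in the primary set is the better reading rather than an explicit statement.

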6.2 Adverse Event Assessment and Documentation

All subjects who undergo attempted implantation of the Hydrus will be evaluated for adverse events. All adverse events, regardless of severity and whether or not they are ascribed to the Hydrus implant or delivery system, will be recorded using standard medical terminology. All events for the study eye, fellow eye, and non-ocular are to be recorded.

All adverse events will be evaluated beginning with onset, and evaluation will continue until resolution is noted, or until the investigator determines that the subject's condition is stable.

The investigator will take appropriate and necessary therapeutic measures required for resolution of the adverse event. Any medication necessary for the treatment of an adverse event must be recorded.

All AEs will be characterized by the following criteria:

- Event term
- Severity
- Expectedness
- Relationship to study device or procedure
- Outcome
- Treatment or action taken.

Whenever possible, recognized medical terms should be used when recording AEs. Colloquialisms and/or abbreviations should not be used. Only one medical concept, preferably a diagnosis instead of individual symptoms, should be recorded as the event.

If more than one distinct adverse event occurs, each event should be recorded separately.

However, if known at the time of reporting, a diagnosis (i.e., disease or syndrome) should be recorded rather than individual signs and symptoms (e.g., record congestive heart failure rather than dyspnea, rales, and cyanosis). However, if a constellation of signs and/or symptoms cannot be medically characterized as a single diagnosis or syndrome at the time of reporting, each individual event should be recorded as a separate AE. A diagnosis that is subsequently established should be reported as follow-up information. However, signs and symptoms that are considered unrelated to an encountered syndrome or disease should be recorded as individual AEs (e.g., if congestive heart failure and severe headache are observed at the same time, each event should be recorded as an individual AE).

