6.8.1 Anticipated Adverse Events

Anticipated AEs associated with glaucoma surgical procedures that might reasonably be expected to occur in this study are listed below. These specific examples of anticipated AEs include, but are not limited to:

Intraoperative Adverse Events

- Choroidal hemorrhage or effusion
- Corneal abrasion
- Corneal edema
- Cyclodialysis cleft
- Hyphema obscuring the surgeon's view
- Inadvertent perforation of the sclera
- Iridodialysis
- Lens / capsular bag damage (crystalline or IOL)
- Microstent malposition
- Significant iris injury or trauma
- Vitreous loss
- Zonular dialysis

Postoperative adverse events include

- Angle closure
- Angle recession
- Anterior chamber cell or flare requiring either an increase in the standard postoperative steroid regimen or re-initiation of steroid use following completion of the standard postoperative steroid regimen.
- Aqueous misdirection
- Atrophy, phthisis
- Best-corrected visual acuity loss of 2 lines (10 letters) or more compared to baseline on the ETDRS chart measured before or at 1-month postoperative
- Best-corrected visual acuity loss of 2 lines (10 letters) or more compared to baseline on the ETDRS chart measured after 1-month postoperative
- Blebitis
- Choroidal detachment
- Choroidal hemorrhage or effusion (detachment with at least a partially hemorrhagic component that obstructs or causes pain, including both peripheral and "kissing" choroidal detachments) lasting 30 days or less
- Choroidal hemorrhage or effusion (detachment with at least a partially hemorrhagic component that obstructs or causes pain, including both peripheral and "kissing" choroidal detachments) lasting longer than 30 days
- Chronic anterior uveitis defined as inflammation of grade 1+ or worse persisting for more than 90 days postoperatively or that recurs less than 90 days after discontinuing standard medication regimen
- Chronic pain in the study eye onset ³ 3-months postoperative
- Corneal decompensation

- Corneal edema persisting > 30 days (mild to moderate) or severe corneal edema ≥ 1 day.
- Corneal opacification
- Descemet's membrane detachment
- Device migration (dislodgement or movement)
- Device obstruction
- Elevated mean IOP ≥ 10 mmHg than the qualifying baseline mean IOP onset before or at 1-month postoperative
- Elevated mean IOP ≥ 10 mmHg than the qualifying baseline mean IOP onset after 1-month postoperative
- Endophthalmitis

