- Flat anterior chamber with lens/cornea touch or shallow anterior chamber with peripheral iridocorneal apposition
- Hyphema ≥ 2 mm in height (layered) at any time
- Hyphema present or arising > 30 days postoperative
- Hypotony (defined as IOP < 6 mmHg) onset before 1-month postoperative
- Hypotony (defined as IOP < 6 mmHg) onset at or after 1-month postoperative
- Implant corneal touch
- Implant-iris touch associated with intraocular inflammation, pigment dispersion, or other sequelae
- Inadvertent bleb
- Increase in vertical C/D ratio of ≥ 0.3 units from screening on fundus examination
- Iris prolapse/wound incarceration
- Maculopathy including hypotonic maculopathy
- Persistent diplopia
- Pupil block
- Retinal complications (e.g., flap tears, retinal break, retinal detachment, age related macular degeneration, diabetic retinopathy, macular edema, epiretinal membrane, central serous retinopathy, or proliferative vitreoretinopathy)
- Scleral ectasia
- Surgical re-intervention in the study eye (other than paracentesis to relieve pressure within the 1 week visit)
- Toxic anterior segment syndrome (TASS)
- Vitreous haze
- Vitreous hemorrhage
- Vitritis
- Worsening of 2-points (from screening) to "severe" on the slit lamp examination findings (other than cells and flare) onset at or after 3-months postoperative not associated with a pre-existing condition
- Worsening of lens opacities (defined as a 2.0 or more score change on at least one category of the LOCS III grading system, at 2 or more consecutive visits)
- Worsening of visual field (mean deviation worsening by 3.0 dB or more, confirmed by 2 repeat measurements)
- Wound dehiscence (persistent aqueous leak or fistula formation)

For any adverse event that may be due to incorrect device positioning (i.e. vitreous hemorrhage, hyphema, hypotony), gonioscopy should be performed to assess the device position. If the position cannot be adequately evaluated by gonioscopy, ultrasound biomicroscopy (UBM) should be performed.

For slit lamp examination, gonioscopy and fundus findings for which there is no grading scale, any finding considered by the study investigator to be marked or severe, i.e., clinically significant, should be recorded as an Adverse Event.

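### Footnote 6 conflicts with 6.2 and 6.6 on following non-device-related adverse events open at 1 month in eyes not implanted, and 5.4 names no denominator for late events

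*Combined protocol and SAP*

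**What the plan says.** On follow-up:

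- Section 4.0, main text: "All subjects will be scheduled to return for follow-up examinations at defined intervals through 12 months".
- Section 4.0, footnote 6: "Subjects who do not receive the microstent during surgery will be followed for safety for 1 month postoperatively or until the device-related adverse event". The rest of the sentence makes the second limb conditional on there being such an event and ends it at resolution or stability. It does not say which limb prevails when they differ.
- Section 6.2, on who is covered: "All subjects who undergo attempted implantation of the Hydrus will be evaluated for adverse events". On what is captured: "All adverse events, regardless of severity and whether or not they are ascribed to the Hydrus implant or delivery system, will be recorded". On how long: "All adverse events will be evaluated beginning with onset, and evaluation will continue until resolution is noted", or until the investigator judges the condition stable.
- Section 6.6 has ongoing events followed after study exit until they resolve, stabilize or are judged unable to resolve. It adds that significant study-eye events present at the exit visit should be followed by the physician. Neither sentence is limited to device-related events.

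On analysis:

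- Section 5.1: "The Safety Population includes all subjects for whom a Hydrus microstent was implanted or implantation was attempted".
- Section 5.4 summarizes adverse events by counts and percentages, divides them only into intraoperative and postoperative, and reports relationship to both device and procedure. It names no population or denominator and makes no adjustment for length of observation.
- Section 6.8.1 defines several anticipated events by late onset or long duration, for example "Chronic anterior uveitis defined as inflammation of grade 1+ or worse persisting for more than 90 days postoperatively" and "Hyphema present or arising > 30 days postoperative".

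**The concern.** There are two separate issues.

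The first is a conflict of instructions. A site with an unimplanted eye and an unresolved event at 1 month finds one rule in footnote 6 and another in 6.2 and 6.6, unless the event is device-related. If sites follow the footnote, the outcome of a persistent surgical injury may go unrecorded, and no later analysis can recover it.

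The second is a denominator question. Subjects whose scheduled visits end at about 1 month are still in the Safety Population. If late events are expressed as a percentage of that population, these subjects count as event-free for a period in which nobody examined them.

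**Working it through.** **Step 1. Set the follow-up rules side by side** for a subject with an attempted but failed implantation and an event still open at 1 month.

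| Open event at 1 month | Footnote 6 | 6.2 and 6.6 |
|---|---|---|
| Device-related | Continues to resolution or stability, if the two limbs mean whichever is later | Continues |
| Procedure-related, not device-related | May end at 1 month | Continues |
| Related to neither | May end at 1 month | Continues |

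The second and third rows conflict. The first agrees only if 1 month is a minimum, which the footnote leaves open.

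**Step 2. Identify the late items.** Nine items in 6.8.1 have a criterion at or beyond 1 month or 30 days.

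- Five turn on late onset or late measurement: visual acuity loss after 1 month, IOP elevation after 1 month, hypotony from 1 month, chronic pain from 3 months, and slit-lamp worsening from 3 months.
- Four can be met by persistence of an earlier event: choroidal hemorrhage or effusion beyond 30 days, corneal edema beyond 30 days, anterior uveitis beyond 90 days, and hyphema beyond 30 days. Three of these have another limb: corneal edema also qualifies if severe for a day or more, uveitis may qualify by recurrence, and hyphema may newly arise after day 30.

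The 1-month visit window is 30 ± 7 days, so the last scheduled visit falls between day 30 − 7 = 23 and day 30 + 7 = 37. Some onset items, such as hypotony, could be caught at that visit. The 3-month items could not.

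**Step 3. Size the denominator effect.** The documents give no failed-implantation rate, late-event rate or sample size, so there is no stated figure to reproduce. Let f be the share of the Safety Population not implanted and r the late-event rate among subjects followed to 12 months; both are assumptions. If no late event is observed in the failed eyes:

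reported rate = r × (1 − f)

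If a share q of the failed eyes stays in follow-up with the same late risk:

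reported rate = r × (1 − f × (1 − q))

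| f (assumed) | r = 10%, q = 0 | r = 20%, q = 0 | r = 10%, q = 0.5 |
|---|---|---|---|
| 2% | 9.8% | 19.6% | 9.9% |
| 5% | 9.5% | 19.0% | 9.75% |
| 10% | 9.0% | 18.0% | 9.5% |

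For example, 10% × (1 − 0.10) = 9.0%, and with half retained 10% × (1 − 0.10 × 0.5) = 9.5%. With equal late risk, the relative understatement is f when q = 0 and less otherwise. Dividing by subjects still under observation gives back r.

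**Step 4. Treat implant-dependent events separately.** An eye without a microstent cannot have device migration or obstruction. Longer follow-up would not change that; only a denominator of implanted subjects gives the rate among those at risk.

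**The case against.** The strongest reply is that the documents work if read together: footnote 6 sets the period of scheduled visits, and 6.2 and 6.6 govern any event still open when those visits end. On that reading a persistent injury is not lost. Much of this stands. A reader might infer that injured eyes simply leave follow-up at 1 month, and 6.6 does not support that. A reader might also infer that ending scheduled visits at 1 month contradicts 6.2. It does not: 6.2 sets no calendar period for finding new events, and the footnote can be a deliberate exception to the 12-month schedule in 4.0. The reply does not remove the conflict over open events, because the footnote gives its own rule for extension and confines it to device-related events.

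Second, cannula injuries may themselves be device-related, since section 1.0 describes the delivery system as a device and 6.1 and 6.2 name it alongside the implant. That narrows the gap. It remains for injuries due to the surgery but not to the delivery system, and for unrelated events.

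Third, it is tempting to say that every late percentage is diluted. Section 5.4 supports no such statement: it names no denominator and plans no early/late split, and persistence items can still be captured through 6.2 and 6.6. The dilution is conditional and mainly concerns new-onset late items. Higher late risk in failed eyes would enlarge the shortfall relative to the whole population, but the documents give no evidence of it. The safety summaries are descriptive, so no test or threshold depends on the percentages.

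**Conclusion.** The point holds in a limited form. Footnote 6 conflicts with 6.2 and 6.6 for events open at 1 month, in subjects not implanted, that are procedure-related or otherwise not device-related. Whether 1 month is a minimum is also unstated. This is the more important half, because it bears on whether safety outcomes are collected at all.

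The denominator effect is secondary and modest. It rests on three assumptions: the Safety Population is the denominator in 5.4, failed eyes carry the same late risk as the others, and none of them is observed late. Under these, a 10% rate loses 0.2 to 1.0 percentage points for f between 2% and 10%, and less if some failed eyes remain in follow-up. The actual size cannot be determined from the documents. The change should be made: it is cheap and improves the completeness and interpretability of the safety data.

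**What to change.** 1. Reconcile footnote 6 with 4.0, 6.2 and 6.6 so that one rule states which open events extend follow-up of subjects not implanted, and whether 1 month is a minimum. Which rule applies is for the sponsor and investigators to decide; this review does not propose one.
2. In 5.4, name the denominator. For items defined at or beyond 1 month, use subjects still under observation in the relevant window. For events that require an implant, such as migration and obstruction, use implanted subjects.
3. List the adverse events and outcomes of attempted-only subjects separately. This matters because any who remain under observation may do so because of an open event, so their late experience should be visible and not only pooled.

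The cost is a wording change in the protocol and SAP, one more denominator column and a short listing. Late-event percentages may look slightly less favorable, and a few subjects may be followed longer, depending on the rule chosen.
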